** Participants will use this DC1 to record information about solicited reactions, unsolicited AEs, SAEs, and AESIs from D01 to D08 after vaccination and will continue to record information about unsolicited AEs, SAEs, and AESIs from D09 to V02.

†† The Investigator or an authorized designee will remind the participants to bring back the DC at the next visit and will answer any questions.

‡‡ The Investigator or an authorized designee will interview the participants to collect the information recorded in the DC and will attempt to clarify anything that is incomplete or unclear.

§§ Participants will use this DC2 to record solicited reactions, unsolicited AEs, SAEs, and AESIs (from V02 to V03) and will continue to collect unsolicited AEs, SAEs, and AESIs (from V03 to V04).

*** Participants will use this DC3 for unsolicited AEs follow-up until D43 and SAEs, AESIs, and COVID-19-like illness follow-up from V04 to V05.

††† Participants will use this DC4 for SAEs, AESIs, and COVID-19-like illness follow-up from V05 to V06.

‡‡‡ Participants will use this DC5 for SAEs, AESIs, and COVID-19-like illness follow-up from V06 to V07.

§§§ During the D09 telephone call, staff will review the DC1 for solicited reactions from D01 to D08 after vaccination, inquire whether the participant experiences any SAE or AESI not yet reported, and remind the participant to bring back DC1 for V02. This telephone call will NOT be documented in the CRF.

**** Prior to these specified time-points, active surveillance will still occur during the established contacts (phone calls and visits).

†††† AESIs (serious and non-serious) will be collected throughout the study as SAEs to ensure that events are communicated to the Sponsor in an expedited manner and followed-up until the end of the follow-up period or resolution, as per the assigned causal relationship. These include: Anaphylactic reactions, Generalized convulsion, Thrombocytopenia, Lacrimal and salivary disorders (tearing, dry mouth, dry eyes), any new-onset chronic medical conditions, and potential immune-mediated diseases.

†††† In case of participant discontinuation at a visit, the entire visit will be completed.

§§§§ During the D43 telephone call, staff will review the DC3 pertaining to unsolicited AEs, SAE, AESI, and COVID-19-like illness between V04 and the call and will remind the participant to bring back the DC3 for V05. This telephone call will NOT be documented in the CRF.

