8.4.1 Time Period and Frequency for Collecting AE and SAE Information

Immediate Post-vaccination Observation Period

Participants will be kept under observation for 30 minutes after each vaccination to ensure their safety. The post-vaccination observation should be documented in the source document.

Reactogenicity

Solicited injection site reactions will be collected from D01 to D08 after each vaccination.

Solicited systemic reactions will be collected from D01 to D08 after each vaccination.

The solicited injection site reactions and systemic reactions that are pre-listed in the diary cards and CRF, together with the intensity scales, are presented in [Appendix 10.3.5.1.1](#).

Unsolicited Adverse Events

Unsolicited AEs include unsolicited non-serious AEs and SAEs. The intensity grading scale for unsolicited non-serious AEs is presented in [Appendix 10.3.5.1.2](#).

Unsolicited non-serious AEs will be collected from D01 to D22 after each vaccination.

SAEs will be collected and assessed throughout the study, from inclusion until 12 months after the last vaccination (up to D366 for Cohort 1 and up to D387 for Cohort 2). However, before the first study intervention administration, only SAEs related to study procedures are to be collected (eg, SAEs related to blood sampling).

Medical occurrences that begin before the start of study intervention but after obtaining informed consent will not be recorded on the AE section of the CRF.

All SAEs will be recorded and reported to the Sponsor or designee immediately and under no circumstance should this exceed 24 hours, as indicated in [Appendix 10.3](#). The Investigator will submit any updated SAE data to the Sponsor within 24 hours of it being available.

Investigators are not obligated to actively seek AE or SAE after conclusion of the study participation. However, if the Investigator learns of any SAE, including a death, at any time after a participant has been discharged from the study, and he/she considers the event to be reasonably related to the study intervention or study participation, the Investigator must promptly notify the Sponsor.

Medically Attended Adverse Events (MAAEs)

MAAEs will be collected at any time during the study.

Adverse Events of Special Interest (AESIs)

AESIs will be collected at any time during the study.

See [Section 8.4.6](#) for the list of AESIs.

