All participants will receive 1 injection of either one of the investigational study vaccine formulations or the placebo control at Day (D)01 (Vaccination [VAC] 1). Participants in Cohort 2 will receive a second injection of study vaccine formulation or placebo at D22 (VAC2). Participants are planned to be followed approximately 365 days post-last dose

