4.4.1.2.4 Time of Onset

Time of onset is derived from the start date of the unsolicited AE provided in the clinical database and the date of last vaccination as described in [Section 4.4.1.2.2](#):

Time of Onset = start date of the unsolicited AE – date of last vaccination before the unsolicited AE + 1

The time of onset should be considered as missing only if one or both of the dates are missing or partially missing.

The unsolicited AEs will be analyzed “Within 21 days”, which corresponds to AEs with a time of onset between 1 and 22 days or missing.

An AE with missing time of onset will be considered to have occurred just after the vaccination indicated by the visit number in “Appeared after visit” or similar field, so will be included in these tables.

Time of onset will be displayed as follows:

- D01-D04
- D05-D08
- D09-D15
- D16 or later
- Missing

Note: To further clarify the analysis:

- Any unsolicited AEs reported up to the entire study period (SAEs, MAAEs, AESIs) with time of onset > 22 days after each injection will not be presented in tables of unsolicited AEs within 21 days but only in tables of SAEs, MAAEs, AESIs and NOCMCs.

- Any unsolicited AEs reported up to 21 days with time of onset between 1 and 22 days or missing after each injection will be presented in the tables of unsolicited AEs within 21 days.
- Any unsolicited AEs reported up to 21 days with time of onset > 22 days after each injection will not be presented in any tables but listed separately.
- Any unsolicited AEs with null (0) or negative time of onset will be excluded from the above tables and listed separately

Safety analysis will include only those unsolicited AEs with time of onset before a participant received a non-study authorized/approved COVID-19 vaccine if applicable. Events with time of onset on or after the date of receiving a non-study authorized/approved COVID-19 vaccine will be listed separately.

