4.4.1.2.6 Serious Adverse Event (SAE)

SAEs will be analyzed throughout the study using the following periods:

- During post-Dose 1 period (i.e., between injection 1 and injection 2), and during 21 days after the last injection
- During the 6-month follow-up period
- During the 12-month follow-up period

- During the study (i.e., all SAEs occurred during the study)

Additionally, a table will present all SAEs during the study in order to count all SAE collected.

Note: SAE that occurred before vaccination (negative time of onset) will not be included in analysis, but will be listed separately.

Safety analysis will include only those SAEs with time of onset before a participant received a non-study authorized/approved COVID-19 vaccine, if applicable. SAEs with time of onset on or after the date of receiving a non-study authorized/approved COVID-19 vaccine will be listed separately.

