5.1.1.2 Statistical Methods for Primary Safety Objective

Safety results will be described for each age and vaccine group. The homogeneity of pooled groups will be assessed on the main parameters. The main parameters will be described with 95% CI.

Safety analyses will be performed based on safety analysis set including safety data collected before the date of receiving an authorized/approved COVID-19 vaccine. Safety data collected on or after the day of receiving an authorized/approved COVID-19 vaccine will be listed separately.

Solicited Reactions

Number and percentage of subjects with:

- Presence of solicited injection site reactions and systemic reactions occurring up to 7 days after injection
- Each solicited reaction according to time of onset, maximum intensity, and number of days of occurrence over the solicited period

Unsolicited Events and Reactions

Number and percentage of subjects with:

- Any unsolicited immediate systemic event in the 30 minutes after injection
- Any unsolicited event and reaction (using the current MedDRA version) 21 days after injection
- Any unsolicited event/reaction according to time of onset, maximum intensity, and duration

SAEs

Number and percentage of subjects with:

- any SAE within 21 days after injection and during the 6 months and 12 months follow-up periods according to SOC and PT, seriousness and outcome

AEs of special interest

- Number and percentage of subjects with any/each AESI within 21 days after injection and during the 6 month and 12 months follow-up periods will be presented according to SOC and PT, seriousness and outcome.

MAAE

- Presence of medically attended adverse events (MAAEs) throughout the study

Laboratory tests

- Presence of out-of-range biological test results up to 7 days post-last dose (ie, up to D09 for Cohort 1 and up to D30 for Cohort 2)

The following analyses will be performed for laboratory tests in addition to the summary of out of range tests above:

- Biological test results and toxicity grade by visit,

- Summary of toxicity grade shift from baseline,

For descriptive purposes, the statistics presented on [Table 5.1](#) will be produced.

In addition to analyses by each intervention group, aggregated groups will be used to perform complementary assessments for above parameters, including:

1. aggregated vaccine group, ie, all vaccine arms pooled
2. aggregated placebo group, ie, two placebo arms pooled

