5.2.2 Safety Analysis Set

Subset of randomized participants who have received at least one injection of study intervention. Participants will have their safety analyzed according to the study intervention they actually received. All subjects will be analyzed after each dose according to the vaccine they actually received, and after any dose according to the vaccine received at the 1st dose.

Safety data recorded for a vaccine received out of the protocol design will be excluded from the analysis (and listed separately).

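### Pooled safety columns mix the one- and two-injection cohorts in unequal proportions, so after-any-injection percentages are expected to be higher for vaccine than placebo, and for AS03 than AF03, at equal per-injection risk

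*SAP*

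**What the plan says.** **Collection.** Protocol 8.4.1: "Unsolicited non-serious AEs will be collected from D01 to D22 after each vaccination". Cohort 1 therefore has one window. Cohort 2 has two, and the footnotes to its schedule (Protocol 1.3, Table 1.2) carry collection on: "Participants will use this DC3 for unsolicited AEs follow-up until D43". Solicited reactions likewise have one collection period per injection.

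**Analysis window.** SAP 4.4.1.2.4 counts unsolicited events within 21 days of the last preceding vaccination, "which corresponds to AEs with a time of onset between 1 and 22 days or missing".

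**Tabulation.** SAP 5.2.2 assigns participants to groups for tables after each dose, and also "after any dose according to the vaccine received at the 1st dose". For SAEs, SAP 4.4.1.2.6 lists as its first period: "During post-Dose 1 period (i.e., between injection 1 and injection 2), and during 21 days after the last injection". AESIs (4.4.1.4.7) and MAAEs (4.4.1.4.8) have the same first period.

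**Pooling.** SAP 5.1.1.2 describes safety by age and vaccine group. It then applies the same parameters to four kinds of aggregate, overall and by age: vaccine ("aggregated vaccine group, ie, all vaccine arms pooled"), both placebo arms, dose level and adjuvant type. None is defined within a cohort. Homogeneity of pooled groups is to be assessed, but neither a method nor a consequence is given.

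**The concern.** The percentage of participants with at least one event after any injection depends on how many injections, and so how many windows, each participant has. If two pooled columns contain the same proportion of two-injection participants, this affects both alike. If the proportions differ, the column with more two-injection participants is expected to show a higher percentage even when every product carries the same risk per injection.

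Placebo is split equally between the cohorts. The vaccine arms are not, because the two Cohort 2 AS03 arms have 90 participants each and the unadjuvanted arm exists only in Cohort 2. A reader who sets the pooled vaccine column beside the pooled placebo column, or AS03 beside AF03, would take part of the cohort mix for a product effect.

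**Working it through.** **Inputs (Protocol Table 4.2).** Ages 18-49: 9 arms × 20 + 2 × 60 = 300. Ages 50 and over: 8 × 10 + 2 × 30 = 140. The total is 440, as SAP 5.5 states. The group sizes in SAP 5.1.1.4 also reproduce (for example AS03 240, AF03 120, one injection 120, two injections 240).

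**Cohort mix of the safety pools.**

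| Pool | Cohort 1 | Cohort 2 | Two-injection share w |
|---|---|---|---|
| All vaccine | 120 | 260 | 68.4% |
| Placebo | 30 | 30 | 50.0% |
| AS03 | 60 | 180 | 75.0% |
| AF03 | 60 | 60 | 50.0% |
| Low dose | 60 | 120 | 66.7% |
| High dose, with unadjuvanted arm | 60 | 140 | 70.0% |

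By age, vaccine against placebo is 180/260 = 69.2% against 50% (18-49) and 80/120 = 66.7% against 50% (50 and over).

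**Nominal unsolicited collection time**, (22·n1 + 43·n2)/n: vaccine (22×120 + 43×260)/380 = 36.4 days; placebo (22×30 + 43×30)/60 = 32.5 days. The 43 days are nominal, because the second injection has a +7-day visit window.

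**Model.** Let p be the probability of at least one event in a window, the same in every arm, with windows independent. The after-any-injection percentage is p in Cohort 1 and 1−(1−p)² in Cohort 2. A pool with share w has

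(1−w)·p + w·[1−(1−p)²],

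and two pools differ by (w_a − w_b)·p(1−p). The documents state no event rate, so p is shown over a range.

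| p | Vaccine | Placebo | Excess (points) | AS03 | AF03 | Excess (points) |
|---|---|---|---|---|---|---|
| 0.10 | 16.2% | 14.5% | 1.7 | 16.75% | 14.5% | 2.25 |
| 0.20 | 30.9% | 28.0% | 2.9 | 32.0% | 28.0% | 4.0 |
| 0.30 | 44.4% | 40.5% | 3.9 | 45.75% | 40.5% | 5.25 |
| 0.50 | 67.1% | 62.5% | 4.6 | 68.75% | 62.5% | 6.25 |

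At p = 0.20, for example, vaccine is (120×20% + 260×36%)/380 = 30.9%. Because p(1−p) peaks at 0.50, the last row is the maximum. For the dose-level pools the difference at p = 0.20 is (0.700 − 0.667)×0.16 = 0.5 points.

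**Sensitivity.** If second-window risk is r·p, the excess becomes (w_a − w_b)·r·p(1−p). With r = 0.5 every excess halves (1.5 points for vaccine-placebo at p = 0.20), and the direction is unchanged.

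**Sampling error at p = 0.20.**
- Vaccine-placebo: variance = (120×0.16 + 260×0.2304)/380² + (30×0.16 + 30×0.2304)/60² = 0.00055 + 0.00325, so the SD is about 6.2 points.
- AS03-AF03: variance = (60×0.16 + 180×0.2304)/240² + (60×0.16 + 60×0.2304)/120² = 0.00089 + 0.00163, so the SD is about 5.0 points.

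**After the fix.** Within a cohort, or with the same cohort weights in both columns, w_a = w_b and the expected difference under equal risk is zero at every p.

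**The case against.** The case against has four main parts.

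- **The pools are secondary.** The primary safety objective is to describe each age and intervention group. The pools are complementary and descriptive, with a confidence interval for each percentage, and no vaccine-placebo safety difference is specified. The by-arm tables already contain each cohort's own placebo arm (Groups 5 and 11). All of this stands.
- **The effect is small.** The vaccine-placebo excess stays below the sampling SD. In simulation with no product effect at p = 0.20, vaccine exceeded placebo in about 68% of trials, not in all of them. This stands too, but the bias has a known direction and can be removed with data already collected.
- **The table is partly inferred.** No sentence expressly orders an after-any-injection table for the pools; it follows from reading SAP 5.2.2 together with the instruction in 5.1.1.2 to pool the listed parameters. The early SAE/AESI/MAAE bullet could mean two separate periods. In that case the 21 days after the last injection have the same length in both cohorts, and only a combined period is affected. This is a fair limit.
- **The homogeneity check may catch it.** With no method or consequence stated, it cannot be relied on, and it does not equalise cohort mix.

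A reader might also infer that these tables decide the formulation or schedule. The documents do not support that. An all-vaccine pool cannot separate formulations, the safety aggregates include no schedule grouping, and the interim package in SAP 5.4 includes the unaffected by-arm tables. A one- against two-injection contrast (30% against 51% at p = 0.30) is therefore not a planned pooled safety comparison.

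**Conclusion.** The point holds as a modest, avoidable bias in complementary tables. The cause is unequal cohort mix; different collection time by cohort would not by itself bias a pooled comparison. It affects the pooled after-any-injection percentages for vaccine against placebo and AS03 against AF03, and the early SAE/AESI/MAAE period if that is tabulated as one period running to 21 days after the last injection. The dose-level pools are nearly balanced.

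The sizes rest on an assumed p, independent windows and equal risk in both windows. They are expectations: an individual trial could show the reverse order. It is also tempting to say that a real vaccine-placebo difference is shifted by the amount calculated under equal risk. It is not. The shift is (w_v − w_p)·p_v(1−p_v), which depends on the vaccine arms' own rate p_v: with 0.50 for vaccine and 0.20 for placebo it is 4.6 points, not 2.9.

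**What to change.** In SAP 5.1.1.2, for the aggregated vaccine, placebo and adjuvant-type groups:

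1. Present after-any-injection summaries, and the early SAE/AESI/MAAE period, by cohort. Alternatively, combine the cohorts with one fixed set of cohort weights used in both columns being compared.
2. Report any unweighted pool across cohorts per injection only: after injection 1 for all participants, after injection 2 for Cohort 2.
3. State whether the early SAE/AESI/MAAE bullet is one period or two.

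No new data are needed. The cost is SAP wording, more table columns and smaller columns, with placebo at 30 per cohort. The by-cohort placebo columns will largely repeat Groups 5 and 11, which is a reason to prefer common weights where a single overall figure is wanted. A weighted percentage is not a single binomial proportion, so the SAP would then need to name an interval other than Clopper-Pearson for it.

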As a precautionary step, a Sentinel Safety Cohort of 6 participants (younger adults only) within each dosing group from Cohort 1 will be enrolled. An ESDR will be performed, including evaluation of safety data and laboratory measures to D09 in Cohort 1 among younger adults 18-49 years of age. Upon acceptable safety demonstrated from unblinded review by limited members of the Sponsor Study Team (RMO, Biostatistician and Programmer, Pharmacovigilance Science Expert, and Global Safety Officer), the remaining participants in Cohort 1 and all participants in Cohort 2 will be enrolled. A non-clinical toxicology study in New Zealand White Rabbits is planned and will provide rabbit first-dose safety data prior to initiation of human clinical testing. Additional non-clinical safety evaluations will proceed in parallel to this human clinical trial.

Data up to D43, in addition to preclinical data, will support the selection of a formulation or formulations and dosing schedule to proceed to further testing in Phase III.

Rationale for Injection Schedule

In the setting of a pandemic, a single injection would be ideal to be able to protect vaccinees as early as possible and better manage vaccine supply. However, given the lack of pre-existing immune responses to SARS-CoV-2, it is most likely that 2 injections may be necessary.

A separation of 21 days for the 2-injection schedule is proposed for this program, mirroring the schedule that was evaluated and approved for pandemic influenza vaccines to address the 2009 H1N1 influenza pandemic (AS03 adjuvanted vaccines Pandemrix™, Arepanrix™; and AF03 adjuvanted Humenza vaccine). This schedule results in a second injection of the vaccine being administered earlier than with other common vaccines with longer separations between injections (ie, 28 days), thus aiming at earlier generation of potentially protective immune responses. This may be of particular interest in an ongoing pandemic setting.

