future supply, in the event supply beyond AS03 capacity is possible with the recombinant protein and needed to address the pandemic; 3) the AF03 adjuvant may be of interest in the future if COVID-19 becomes seasonal, in which case a co-formulated vaccine would be attractive; in such circumstances, co-formulation with AF03 will be more feasible than with AS03 as both protein and adjuvant are proprietary to Sanofi Pasteur. The higher priority given to AS03 adjuvanted formulations and the higher likelihood of robust immune responses with a 2-injection schedule provides rationale to generate more precise data for AS03 formulations in Cohort 2 of this Phase I/II study; this is the justification for a sample size of 90 across age groups for the AS03 adjuvanted arms in Cohort 2. All other arms in the study will have a size of 30 total, except for the un-adjuvanted arm which would only comprise 20 younger adults.

Rationale for Blinding

This is an observer-blind study for formulation and adjuvant. Owing to the need for mixing of study formulations from separately supplied antigen, adjuvants, and / or diluent, the person preparing and administering the vaccine will be unblinded to vaccine group assignment. Blinding of all “observers” will minimize the risk of bias arising from the possibility of consciously or unconsciously influencing the reporting of study outcome measures due and knowledge of the formulation administered.

Rationale for Placebo

Placebo, rather than a benefit licensed vaccine, will be used for comparison to vaccine to allow safety comparisons between vaccine and placebo as there are no other licensed COVID-19 vaccines on the market. The inclusion of placebo groups will also maintain the blind, allowing the unbiased evaluation of clinical outcomes related to COVID-19-like illness and SARS-CoV-2 infection by treatment group (secondary efficacy objective).

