9.2 Sample Size Determination

This is a first-in-human study to assess the safety profile and immune responses to different formulations of the study vaccine when compared to placebo. A total of 440 participants will be enrolled. No formal power calculation has been performed. The sample size was determined based on logistical considerations and common practices for first-in-human trials.

Vaccine arms will be aggregated to perform complementary assessments on the following main effects: age [(18-49 years [N=240], \geq 50 years [N=120]), dose (low [N=180], high [N=180]), injection schedule (1-injection [N=120], 2-injection [N=240]), adjuvant type (AS03 [N=240], AF03 [N=120]), overall adjuvant (high-dose with adjuvants [N=180], high-dose without adjuvants [N=20]), and dose-sparing adjuvant (low-dose with adjuvants [N=180], high-dose without adjuvants [N=20]).

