9.4.1 General Considerations

All analyses will be descriptive. Summaries will be provided for main effects (see [Section 9.2](#)) as well as individual study arms. Details will be provided in the SAP.

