9.4.2.2 Safety

The primary endpoints for the evaluation of safety are as presented in [Table 3.1](#).

Primary safety endpoints will be summarized by vaccine group, as well as aggregate groups specified in the SAP. The 95% CIs will be calculated using the Clopper-Pearson method.

The SafAS will be used for the safety analyses.

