3. aggregated dose-level group, ie, low-dose arms pooled, or high-dose arms pooled
4. aggregated adjuvant type group, ie, AF03 arms pooled or AS03 arms pooled

The analyses by aggregated groups will also be conducted in overall population and by age group.

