5.1.1.4 Statistical Methods for Primary Immunogenicity Objective

The primary endpoints for the evaluation of immunogenicity are based on neutralizing antibody titers, which will be measured with the neutralization assay. The statistical analyses will be performed for the following primary endpoints below on overall population and by age group:

1. Antibody titer on D01, D22, and D36
2. Fold-rise (fold-rise in serum antibody neutralization titer post-vaccination relative to D01) at D22, and D36
3. 2-fold and 4-fold rise in serum neutralization titer relative to D01 at D22, and D36
4. Occurrence of neutralizing antibody seroconversion, defined as baseline values below LLOQ with detectable neutralization titer above assay LLOQ at D22 and D36.

Vaccine arms will be aggregated to perform complementary assessments on the following main effects. The primary endpoints above will also be summarized for the main effects.

1. age [(18-49 years, \geq 50 years), where the category of 18-49 years (N=240) includes all vaccine arms except high dose no adjuvant arm aged 18-49 years old; the category of \geq 50 years (N=120) includes all vaccine arms aged 18-49 years old.]
2. dose (low, high), where the category of low (N=180) includes vaccine arms of low dose with either AF03 or AS03 adjuvant; the category of high (N=180) includes vaccine arms of high dose with either AF03 or AS03 adjuvant.
3. injection schedule (1-injection, 2-injection), where the category of 1-injection (N=120) includes vaccine arms in cohort 1; the category of 2-injection (N=240) includes vaccine arms in cohort 2 except the high-dose with no adjuvant arm.

4. adjuvant type (AS03, AF03), where the category of AS03 (N=240) includes vaccine arms with adjuvant AS03; the category of AF03 (N=120) includes vaccine arms with adjuvant AF03.
5. overall adjuvant (high-dose with adjuvants, high-dose without adjuvants), where the category of high-dose with adjuvants (N=180) includes vaccine arms of high-dose with either AS03 or AF03; the category of high-dose without adjuvants (N=20) includes the vaccine arm with high-dose and no adjuvant.
6. dose-sparing adjuvant (low-dose with adjuvants, high-dose without adjuvants); where the category of low-dose with adjuvants (N=180) includes vaccine arms of low-dose with either AS03 or AF03; the category of high-dose without adjuvants (N=20) includes the vaccine arm with high-dose and no adjuvant.

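### The SAP's pooled safety groups omit injection schedule, so after-any-injection summaries and the SAE, AESI and MAAE period summaries mix one- and two-injection recipients in every pool

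*SAP*

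**What the plan says.** - Protocol 9.4.1, which covers all analyses: "Summaries will be provided for main effects", with a pointer to Section 9.2, in addition to the individual arms. Details are left to the SAP.
- Protocol 9.2 lists schedule among those effects: "injection schedule (1-injection [N=120], 2-injection [N=240".
- Protocol 9.4.2.2, on safety: "Primary safety endpoints will be summarized by vaccine group, as well as aggregate groups specified in the SAP".
- SAP 5.1.1.4 uses schedule for the primary immunogenicity endpoints: "the category of 2-injection (N=240) includes vaccine arms in cohort 2 except the high-dose with no adjuvant arm".
- SAP 5.1.1.2 introduces the safety pools with "aggregated groups will be used to perform complementary assessments for above parameters, including". It lists all vaccine arms, both placebo arms, dose level and, last, "aggregated adjuvant type group, ie, AF03 arms pooled or AS03 arms pooled". All are produced overall and by age group. No item separates Cohort 1 from Cohort 2.
- SAP 5.2.2 has safety analysed after each dose and after any dose.
- SAP 4.4.1.2.6, 4.4.1.4.7 and 4.4.1.4.8 set the SAE, AESI and MAAE periods: between the injections and 21 days after the last one, the 6-month and 12-month follow-up, and the whole study.
- SAP 5.7 (changes to planned analyses) does not mention dropping schedule from the safety summaries.

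**The concern.** Schedule is one of the choices the trial exists to inform. Protocol 4.2 says that data to Day 43 "will support the selection of a formulation or formulations and dosing schedule to proceed to further testing in Phase III". For immunogenicity the SAP carries the schedule effect through; for safety it does not, and it gives no reason.

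Two things follow for the affected summaries. First, uncommon events (SAEs, AESIs, MAAEs) under a two-injection course can be read only from single arms, although up to 240 comparable recipients exist. Second, the listed pools carry different proportions of two-injection recipients. A difference between AS03 and AF03, or between vaccine and placebo, can therefore arise in part from schedule, and no pooled row would let the reader see that.

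**Working it through.** **Inputs.** Planned arm sizes from protocol Table 4.2 (younger + older). Cohort 1: four adjuvanted arms and placebo, each 20+10. Cohort 2: two AF03 arms of 20+10, two AS03 arms of 60+30, one unadjuvanted arm of 20+0, placebo 20+10. Protocol 4.2 confirms the largest arm size: "this is the justification for a sample size of 90 across age groups for the AS03 adjuvanted arms in Cohort 2". The interval method is Clopper-Pearson (protocol 9.4.2.2).

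**1. Reproduce the plan's schedule groups.** One injection, adjuvanted: 4 × 30 = 120. Two injections, adjuvanted: 30 + 90 + 30 + 90 = 240. Both match protocol 9.2.

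**2. Composition of the listed safety pools.**

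| Pool | Total | Cohort 1 | Cohort 2 | Two-injection share |
|---|---|---|---|---|
| All vaccine | 380 | 120 | 260 | 68% |
| Placebo | 60 | 30 | 30 | 50% |
| Low dose | 180 | 60 | 120 | 67% |
| High dose, with unadjuvanted arm | 200 | 60 | 140 | 70% |
| High dose, adjuvanted only | 180 | 60 | 120 | 67% |
| AF03 | 120 | 60 | 60 | 50% |
| AS03 | 240 | 60 | 180 | 75% |

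**3. Which tables mix schedules.**
- After dose 2: only Cohort 2 has a second injection, so pooled rows hold two-injection recipients only (up to 260 for all vaccine, 180 AS03, 60 AF03). Not mixed.
- Laboratory results by visit: the Day 30 sample is Cohort 2 only (protocol Table 8.1). Not mixed.
- After any injection: Cohort 1 and Cohort 2 appear together in every pool. Mixed.
- SAE, AESI and MAAE in the 21 days after the last injection: the last injection is the first in Cohort 1 and the second in Cohort 2. Mixed.
- The same events over 6 months, 12 months and the whole study: mixed.

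**4. Precision in the mixed tables.** For zero events in n, the upper limit of the two-sided 95% interval is 1 − 0.025^(1/n).
- n=30 (AF03 two-injection arm): 11.6%
- n=90 (AS03 two-injection arm): 4.0%
- n=240 (adjuvanted two-injection pool): 1.5%
- n=120 (adjuvanted one-injection pool): 3.0%

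The chance of at least one case is 1 − (1 − p)^n. The documents give no event rate, so p is an assumption. At p=1% the chance rises from 59.5% (n=90) to 91.0% (n=240); at p=2%, from 83.8% to 99.2%.

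**5. Effect of unequal schedule mix.** Let d be the difference in event percentage between two injections and one, and assume the adjuvants do not differ at all. The pooled AS03 percentage still exceeds the pooled AF03 percentage by (0.75 − 0.50) × d = 0.25d. On the same reasoning, all vaccine exceeds placebo by (0.684 − 0.50) × d = 0.184d, where 0.684 = 260/380.

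**6. Balance within adjuvant.** AF03: 30 low and 30 high dose in each schedule. AS03: 30 and 30 with one injection, 90 and 90 with two. Younger to older is 2:1 throughout. Dose and age mix therefore match across schedules within each adjuvant.

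**The case against.** A reader might infer that two-injection safety is shown only in single arms, or that no pooled row describes safety after two injections. The documents do not support this. SAP 5.2.2 calls for analysis after each dose, and the pools apply to the same safety parameters, so the post-dose-2 rows pool up to 260 two-injection vaccine recipients. For solicited reactions, unsolicited events and Grade 3 events after the second injection, the existing all-vaccine pool already gives a zero-event limit of 1.4% (n=260), slightly tighter than the proposed 240. These rows also cover the 21 days after the second injection, up to Day 43.

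A reader might also infer that the SAP breaks a firm promise. Protocol 9.4.1 is a general statement, 9.4.2.2 leaves the safety aggregates to the SAP, and the SAP list is worded as open. This is an unexplained gap rather than a contradiction.

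Further, everything is descriptive, each arm is schedule-specific, and the AS03 arms were enlarged on purpose. The protocol and SAP record that a partial database lock has taken place, and the SAP says this formulation is not being pursued.

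What stands: post-dose-2 rows include only people who received a second injection. Protocol 7.1.2 stops vaccination after a significant allergic reaction, a related SAE or certain related Grade 3 events, so those rows do not describe the whole two-injection course. No listed pool sets one injection against two. An open list leaves the schedule pool optional and its definition to be chosen after the data are seen. The SAP uses the end of development only to explain why efficacy analyses may be dropped; safety to 12 months after the last dose remains a primary objective.

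**Conclusion.** The gap is real but limited to summaries after any injection and the SAE, AESI and MAAE period summaries. In these, every listed pool mixes schedules, with one-injection recipients making up 25% to 50% of each, and only single arms of at most 90 isolate the two-injection course. A schedule pool would lower the zero-event upper limit from 4.0% or 11.6% to 1.5%, and would show how much of a pooled adjuvant or vaccine-placebo difference could reflect schedule.

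The figures assume planned enrolment with everyone contributing. Safety data from the day of a non-study COVID-19 vaccine onward are excluded (SAP 4.4.1), so actual information at 6 and 12 months may be less.

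The matched dose and age mix within adjuvant might suggest an unconfounded comparison of schedules. The documents do not support that: schedule is unblinded; 24 of the 120 one-injection vaccine recipients (4 arms × 6) are younger sentinel participants enrolled before the rest; and two injections bring two reaction windows and about 21 more days in the study (386 against 365). The rows would be descriptive. This is an inexpensive improvement and does not invalidate the planned safety analysis.

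**What to change.** Add a fifth item to the list in SAP 5.1.1.2: *aggregated injection-schedule group, ie, adjuvanted 1-injection arms (planned N=120) or adjuvanted 2-injection arms (planned N=240) pooled, overall, by age group and within adjuvant (AF03 60 and 60; AS03 60 and 180)*.

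Apply it to the after-any-injection summaries and the SAE, AESI and MAAE period summaries. Show the unadjuvanted arm (20) separately and placebo by schedule (30 and 30) alongside. State how a Cohort 2 participant who received only one injection is classified. Add a footnote giving the limits on comparing schedules: unblinded schedule, earlier sentinel enrolment, two reaction windows and longer participation.

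Record the addition in SAP 5.7, noting that a partial database lock had already taken place. If the sponsor prefers not to add the pool, record the omission and the reason there instead.

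The cost is SAP wording and extra columns in the affected tables. No new data are needed.
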